9.2. Adverse Events

The definitions of an AE or SAE can be found in Appendix 5.

The investigator and any designees are responsible for detecting, documenting, and reporting events that meet the definition of an AE or SAE and remain responsible for following up AEs that are serious, considered related to the study treatment or the study, or that caused the participant to discontinue the study (see Section 8).

9.2.1. Time Period and Frequency for Collecting AE and SAE Information

- All SAEs will be collected from consent until the time point specified in the SoA (Section 2).
- All AEs will be collected from randomisation until the time point specified in the SoA (Section 2).
- Medical occurrences that begin before the start of study treatment but after obtaining informed consent will be recorded on the Medical History/Current Medical Conditions section of the case report form (CRF) not the AE section.
- All SAEs will be recorded and reported to the sponsor or designee within 24 hours, as indicated in Appendix 5. The investigator will submit any updated SAE data to the sponsor within 24 hours of it being available.
- Investigators are not obligated to actively seek AEs or SAEs in former study participants. However, if the investigator learns of any SAE, including a death, at any time after a participant has been discharged from the study, and he/she considers the event to be reasonably related to the study treatment or study participation, the investigator must promptly notify the sponsor.
- The method of recording, evaluating, and assessing causality of AEs and SAEs and the procedures for completing and transmitting SAE reports are provided in Appendix 5.

9.2.2. Method of Detecting AEs and SAEs

Care will be taken not to introduce bias when detecting AE and/or SAE. Open-ended and non-leading verbal questioning of the participant is the preferred method to inquire about AE occurrence.

9.2.3. Follow-up of AEs and SAEs

After the initial AE/SAE report, the investigator is required to proactively follow each participant at subsequent visits/contacts. All SAEs, will be followed until the event is resolved, stabilized, otherwise explained, or the participant is lost to follow-up). Further information on follow-up procedures is given in Appendix 5.

9.2.4. Regulatory Reporting Requirements for SAEs

- Prompt notification by the investigator to the sponsor of a SAE is essential so that legal obligations and ethical responsibilities towards the safety of participants and the safety of a study treatment under clinical investigation are met.
- The sponsor has a legal responsibility to notify both the local regulatory authority and other regulatory agencies about the safety of a study treatment under clinical investigation. The sponsor will comply with country-specific regulatory requirements relating to safety reporting to the regulatory authority, Institutional Review Boards (IRB)/Independent Ethics Committees (IEC), and investigators.
- Investigator safety reports must be prepared for suspected unexpected serious adverse reactions (SUSAR) according to local regulatory requirements and sponsor policy and forwarded to investigators as necessary.
- An investigator who receives an investigator safety report describing a SAE or other specific safety information eg, summary or listing of SAE) from the sponsor will review and then file it along with the Investigator's Brochure and will notify the IRB/IEC, if appropriate according to local requirements.

9.2.5. Cardiovascular and Death Events

For any cardiovascular events and all deaths, whether or not they are considered SAEs, specific Cardiovascular (CV) and Death sections of the CRF will be required to be completed. These sections include questions regarding cardiovascular (including sudden cardiac death) and non-cardiovascular death.

The CV CRFs are presented as queries in response to reporting of certain CV Medical Dictionary of Regulatory activities (MedDRA) terms. The CV information should be recorded in the specific cardiovascular section of the CRF within one week of receipt of a CV Event data query prompting its completion.

The Death CRF is provided immediately after the occurrence or outcome of death is reported. Initial and follow-up reports regarding death must be completed within one week of when the death is reported.

9.3. Safety Assessments

There are no mandated safety assessments, other than monitoring for AEs and SAEs and this is described in Section 9.2.

9.4. Pharmacokinetics

PK parameters are not evaluated in this study.

9.5. Pharmacodynamics

Pharmacodynamic parameters are not evaluated in this study.

9.6. Genetics

Genetics are not evaluated in this study.

9.7. Biomarkers

Biomarkers are not evaluated in this study.

9.8. Health Economics OR Medical Resource Utilization and Health Economics

Health Economics/Medical Resource Utilization and Health Economics parameters are not evaluated in this study.

10. STATISTICAL CONSIDERATIONS

10.1. Hypotheses

The primary purpose of this study is to assess the number of critical errors made by COPD patients, after a subject has read the patient information leaflet(s) (PIL) for each treatment option tested. This is a superiority study.

There are two sub-studies and these will be analysed separately. There is no overlap of subjects and so these are considered independent. Hence there will be no adjustment for multiplicity.

The primary endpoint is the percentage of subjects making at least one critical error after reading the PIL(s) on Treatment Option 1 compared with each of Treatment Option 2 (Sub-study 1) and Treatment Option 3 (Sub-study 2).

For each sub-study, the null hypotheses are no difference between treatment options:

$$H_0: p_1 = p_i; \quad i=2, 3$$

The alternative hypothesis is that there is a difference between treatment options.

$$H_A: p_1 \neq p_i; \quad i=2,3$$

10.2. Sample Size Determination

The sample size calculation for each sub-study is based on the primary endpoint, the percentage of subjects making at least one critical error in each device combination (Ellipta or DISKUS - HandiHaler or Turbuhaler - HandiHaler) after reading the patient information leaflet(s).

Based on the results from studies 201301 and 201330, a range of critical error rates (at least one critical error using each device after reading the patient information leaflet) for each of the treatment options (ELLIPTA, DISKUS - HandiHaler and Turbuhaler - HandiHaler) were explored.

Using 10000 simulations, a total of 72 subjects in each sub-study will provide at least 90% power to show a statistically significant difference between the critical error rate of each of the paired treatment options (Sub-study 1: Treatment option 1 vs. Treatment Option 2; Sub-study 2: Treatment option 1 vs. Treatment Option 3) assuming the following true critical error rates.

Treatment Option 1:	Treatment Option 2:	Treatment Option 3:
ELLIPTA Critical Error Rate	DISKUS - HandiHaler Critical Error rate	Turbuhaler - HandiHaler Critical Error rate
11%	>=37%	>=37%
10%	>=35%	>=35%
9%	>=34%	>=34%
8%	>=32%	>=32%
7%	>=31%	>=31%
6%	>=29%	>=29%

The error rates for the combined treatment options were based on the studies 201301 and 201330 and a conservative assumption that the critical error rate for the combined treatment was the same as the critical error rate for a single device i.e. subjects who made errors made them on both devices.

Conditional logistic regression and a two-sided 5% significance level were used as the analysis method in the simulations. No withdrawal is expected in this single visit study however up to 80 subjects may be randomised to each sub-study to ensure we have 72 evaluable subjects in each sub-study.

10.3. Populations for Analyses

All analysis will be performed by individual sub-study. Each sub-study data may be analysed when the sub-study has completed and the data have been cleaned. The database will be locked when all of the sub-studies have completed and data are cleaned.

For purposes of analysis, the following populations are defined for each sub-study:

Population	Description
All Subjects Enrolled (ASE)	
 All participants who sign the ICF and for whom a record exists in the study database, including screen failures and any subject who was not screened but experienced an SAE between the date of informed consent and the planned date of the Screening visit

Population	Description
Randomised	
 All participants who were randomised.
Intent-to-treat (ITT)	
 All randomised subjects, excluding those who were randomised in error and made at least one critical error assessment from one treatment option device. A subject who is recorded as a screen or run-in failure and also randomized will be considered to be randomized in error. Any other subject who receives a randomization number will be considered to have been randomized. Displays will be based on the treatment to which the subject was randomized.
Safety	
 This population will be the same as the Intent-to-treat population.

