10.4.2. Safety Analyses

All safety analyses will be performed on the Safety Population.

Adverse events (AEs) will be coded using the standard GSK dictionary, Medical Dictionary for Regulatory Activities (MedDRA), and grouped by body system. The number and percentage of subjects experiencing at least one AE of any type, AEs within each body system and AEs within each preferred term will be presented for each treatment group. Separate summaries will be provided for all AEs, drug related AEs, fatal AEs, non-fatal SAEs, AESIs and AEs leading to withdrawal.

Deaths and SAEs, if applicable, will be documented in case narrative format.

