Planned Analyses	
 • No interim analyses are planned for this study. • Sub study 1 and sub study 2 will be reported at the same time. • All decisions regarding final analysis as defined in this RAP document will be made prior to Database Freeze. 																								
Analysis Populations	
 • Subjects Enrolled population (ASE) will consist of all participants who sign the ICF and for whom a record exists in the study database, including screen failures and any subject who was not screened but experienced an SAE between the date of informed consent and the planned date of the Screening visit. All Subjects Enrolled population (ASE) will be used for subject disposition, reason for withdrawal prior to randomisation, inclusion, exclusion and randomisation criteria deviations and SAEs for non randomised subjects. • The Intent-to-Treat population will consist of all randomised subjects, excluding those who were randomised in error and made at least one critical error assessment from one treatment option device. A subject who is recorded as a screen or run-in failure and also randomized will be considered to be randomized in error. Any other subject who receives a randomization number will be considered to have been randomized. The Intent-to-treat population (ITT) will be used for study population, efficacy and safety endpoints. • The Safety population will be the same as the ITT population. 																								

Overview	Key Elements of the RAP
Hypothesis	
For each sub-study, the null hypotheses are no difference between treatment options: $H_0: p_1=p_i; i=2, 3$
 
The alternative hypothesis is that there is a difference between treatment options: $H_A: p_1 \neq p_i; i=2,3$
 
Where treatment $p_1 = \text{ELLIPTA}$, $p_2 = \text{DISKUS} + \text{HandiHaler}$ and $p_3 = \text{Turbuhaler} + \text{HandiHaler}$

Primary Analyses	
 The primary endpoint of the percentage of subjects making at least one critical error after reading the PIL(s) for each treatment option tested will be analysed using conditional logistic regression with subject as fixed strata, and treatment option and period as fixed effects.

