4. ANALYSIS POPULATIONS

Population	Definition / Criteria	Analyses Evaluated
All Subjects Enrolled (ASE)	
 • All participants who sign the ICF and for whom a record exists in the study database, including screen failures and any subject who was not screened but experienced an SAE between the date of informed consent and the planned date of the Screening visit. 	
 • Study population • Reason for withdrawal prior to randomisation
Randomised	
 • All participants who were randomised. 	
 • No formal analysis will be performed on this population
Intent-to-treat (ITT)	
 • All randomised subjects who made at least one critical error assessment from one treatment option device. A subject who is recorded as a screen or run-in failure and also randomised will be considered to be randomised in error provided they have not performed any error assessments. 	
 • Study population • Efficacy • Subject disposition • Safety • Inclusion, exclusion and randomisation criteria deviations
Safety	This population will be the same as the Intent-to-treat population.	

NOTES :

- Please refer to [Appendix 11](#): List of Data Displays which details the population to be used for each displays being generated.

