11.6. Appendix 6: Premature Withdrawals & Handling of Missing Data

11.6.1. Premature Withdrawals

Element	Reporting Detail
General	
 • For reporting purposes, subject study completion will be defined as completion of all three periods (both devices and answered questionnaire) on the day of study visit. • Withdrawn subjects will be defined as those who used at least one device but did not complete all assessments. • Withdrawn subjects will not be replaced in the study. • All available data from subjects who were withdrawn from the study will be listed and all available scheduled data will be included in summary tables and figures, unless otherwise specified.

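### Safety is set equal to ITT and not defined by inhaler use, and the protocol and SAP disagree on who counts as randomised in error, so an exposed subject could, by a narrow route, be missing from the AE tables

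*Protocol*

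**What the plan says.** Protocol 10.3 defines ITT as "All randomised subjects, excluding those who were randomised in error and made at least one critical error assessment from one treatment option device". It then counts any randomised subject who is logged as a screening or run-in failure as randomised in error, without an exception for someone who has already used an inhaler. For Safety it says only: "This population will be the same as the Intent-to-treat population". Protocol 10.4.2 adds: "All safety analyses will be performed on the Safety Population".

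The SAP synopsis (Section 1) repeats the protocol's ITT sentence and its rule: "A subject who is recorded as a screen or run-in failure and also randomized will be considered to be randomized in error". It also states: "The Safety population will be the same as the ITT population".

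SAP Section 4 is different. Its ITT is "All randomised subjects who made at least one critical error assessment from one treatment option device", and a logged failure who was randomised is "considered to be randomised in error provided they have not performed any error assessments". Safety is again the same set as ITT. SAP 2.1 reports a single departure from the protocol's analysis, on the test for the number of instructions, and does not mention this one.

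SAP 11.6.1 foresees device use with incomplete assessment: "Withdrawn subjects will be defined as those who used at least one device but did not complete all assessments".

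**The concern.** A safety population is normally defined by exposure. Here it depends on an efficacy measurement and, in two of the three places, on how the screening record was completed. None of the three definitions asks whether the subject inhaled.

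The risk table in Protocol 3.3.1 names paradoxical bronchospasm, which would follow inhalation at once, and allergic reaction to excipients. For both, the investigator then judges whether the subject continues. Protocol 8.2 requires no assessments after withdrawal during the visit. V0 and V1 may fall on the same day, so screening and first inhalation can be close together. If such a subject falls outside ITT, the event is absent from the AE numerators and the subject from the denominators. That includes Table 3.05, on AEs leading to discontinuation or withdrawal.

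**Working it through.** The plan states no figure that this point changes. The check is a comparison of text, plus a little arithmetic for scale.

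**1. Population behind each safety display**

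- AE Tables 3.01–3.06 (SAP 11.11.3): all ITT.
- Cardiovascular and all-cause death Listings 22–31 (SAP 11.11.6): all ITT.
- AE Listings 08 and 09 (SAP 11.11.5): All Subjects Enrolled (ASE).
- SAP Table 6 also marks listings of non-fatal SAEs, fatal AEs and the coding of AE terms as ASE. Appendix 11 gives numbers only to 08 and 09 among these.
- Deaths and SAEs: case narratives (Protocol 10.4.2).

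**2. Where an exposed subject falls under each rule**

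The protocol sentence, repeated in the SAP synopsis, can be parsed in two ways. In reading A, the assessment is a condition for entering ITT. In reading B, the literal one, it describes the subjects who are excluded. Only one of them can apply. Every row below is a randomised subject who used an inhaler.

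| Logged as screen/run-in failure? | Assessment on record? | Protocol/synopsis, A | Protocol/synopsis, B | SAP Section 4 |
|---|---|---|---|---|
| No | Yes | in | in | in |
| No | No | out | in | out |
| Yes | Yes | out | out | in |
| Yes | No | out | in | out |

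Two results do not depend on the parsing. A logged failure with an assessment is out under the protocol and synopsis on either reading, but in under SAP Section 4. An exposed subject with no assessment is out under SAP Section 4, whatever the screening record says.

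**3. How easily each row is reached**

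- Protocol 6.4 defines a screen failure as someone who consented but was not randomised. A randomised screen failure is therefore an anomaly in the record, although both documents provide for it.
- Under Protocol 9.1.1.1 and 9.1.1.2 the HCP records errors made while the inhaler is being used. SAP 11.6.2.2 counts a blank checklist item as an error, so a partly scored checklist probably counts as an assessment. Having no assessment at all would be unusual.

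**4. Scale**

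- One subject in a sub-study of 80: 1/80 = 1.25%.
- Protocol 3.3.1 gives paradoxical bronchospasm at below 1 in 10,000. Assuming this is a per-subject frequency, 160 × 1/10,000 = 0.016, so fewer than 0.016 cases are expected across both sub-studies.
- Protocol 10.2 allows up to 80 randomised for 72 evaluable per sub-study, and Protocol 5.2 ties evaluable to ITT. The allowance is 80 − 72 = 8 (8/80 = 10%), or 160 − 144 = 16 overall (16/160 = 10%). This is an upper bound on planned non-evaluable subjects, not an estimate of exposed subjects lost.

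**The case against.** The strongest reply is that very little can be lost, and most of it stands.

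- **Ineligible subjects generally stay in.** A reader might infer that anyone found ineligible after inhaling, for example with a hypersensitivity history discovered late, leaves the safety tables. The documents do not support that. Only a logged screening or run-in failure is removed. Other eligibility breaches are criteria deviations, which SAP Section 4 and Table 1.13 place within ITT.
- **A reacting subject will usually have an assessment.** It is tempting to say that AE incidence is selected on tolerating the test. Most checklist steps have been observed by the time a subject has inhaled, and blank items do not void the result, so that goes too far.
- **The event is not lost from the report.** The ASE listings would show it, and a death or SAE would be narrated. What is lost is its count in the tables. A non-serious reaction would be listed without a narrative.
- **SAP Section 4 is the full definition and the synopsis only a summary.** That is a sensible way to settle the conflict, but neither document says so, and the protocol carries the same unqualified rule.
- **SAP 11.6.1 sends withdrawn subjects' available data to the summary tables.** This holds unless otherwise specified. Each AE table specifies ITT, so the provision does not clearly restore a subject who is outside ITT.

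The reply lowers the probability. It does not remove the conflict between the definitions or supply an exposure criterion.

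**Conclusion.** The point holds in a limited form. Safety rests on ITT and not on inhaler use, and the rule for subjects randomised in error differs between SAP Section 4 on one side and the protocol and SAP synopsis on the other, undeclared in SAP 2.1. An exposed subject logged as a screen failure (protocol and synopsis), or without any recorded assessment (SAP Section 4), would be missing from Tables 3.01–3.06 and Listings 22–31.

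Few or no subjects are likely to be affected, and no power, sample-size or efficacy figure changes. The 8-in-80 planning allowance should not be read as a loss of exposed subjects, since Protocol 10.2 expects no withdrawals. Nor can the protocol sentence be held both to require an assessment and to exclude those who have one.

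This rests on three assumptions: a screen-failure record can coexist with randomisation, as both documents foresee; a partly scored checklist counts as an assessment, which the documents imply but do not state; and the displays are run on the populations in their labels.

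**What to change.** - In Protocol 10.3, the SAP synopsis and SAP Section 4, define Safety as all subjects who used, or attempted to use, at least one study inhaler, regardless of eligibility, randomisation error or checklist completion.
- Relabel Tables 3.01–3.06 and Listings 22–31 to that set, and change the ITT default in SAP 9.2.1 to match.
- Keep ITT for efficacy. Replace the ITT wording in Protocol 10.3 and the SAP synopsis with the SAP Section 4 rule, which also removes the ambiguous sentence. If the protocol is not amended, declare the difference in SAP 2.1.

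The cost is wording in three places, one population flag, and new labels on six tables and ten listings. The two sets will usually be identical, so the efficacy analysis and its precision are untouched.

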10.4. Statistical Analyses

10.4.1. Efficacy Analyses

Endpoint	Statistical Analysis Methods
Primary	
The primary endpoint is the percentage of subjects making at least one critical error after reading the PIL(s).
 
This endpoint will be analysed using conditional logistic regression with subject as fixed strata, and treatment option and period as fixed effects. The odds ratio, 95% CI and p-value will be presented for the comparison between treatment options. It will be based on a two-sided hypothesis testing approach of superiority.

Secondary	
The following endpoints will be analysed in the same way as for the primary endpoint if there are sufficient subjects making errors otherwise the data will be summarised only:
 
 The percentage of subjects making at least one critical error after the first instruction from the HCP The percentage of subjects making at least one overall error after reading the PIL(s) The percentage of subjects making at least one overall error after the first instruction from the HCP 
The number of instructions (0, 1 or 2 times) from the HCP which are needed to demonstrate correct inhaler use will be analysed using the Wilcoxon signed rank test.
 
The total amount of time taken to demonstrate correct inhaler use (T1+T2)

Endpoint	Statistical Analysis Methods
	
will be analysed using Kaplan-Meier methods.
 
Treatment preference from questionnaire will be analysed using a Cochran-Mantel-Haenszel test, adjusted for study inhaler use sequence.

Other	
Analysis of the following other endpoints will be defined in the Reporting and Analysis Plan.
 
 • The percentage of subjects making at least one critical error after the second instruction from the HCP • The percentage of subjects making at least one overall error after the second instruction from the HCP • The amount of time taken to read the patient information leaflet and demonstrate correct inhaler device use (T1) • The amount of time taken to be given instruction by the HCP on use of the inhaler and demonstrate correct inhaler use (T2)

